Once romiplostim or dexamethasone is stopped after 365 days since randomization, patients should be clinically evaluated minimum every 4±1 weeks for 6 months (180 days) and continuation of treatment should be decided on an individual basis by the treating physician. At specified visits outlined in the Study Schedule, patients will undergo physical exams including measurement of vital signs (respiratory rate, body temperature, blood pressure, and pulse rate), height (only at screening visit) and weight, blood counts with absolute and relative differential (neutrophil, lymphocyte and monocyte) blood chemistry profiles (serum creatinine, ALT, AST, GGT, K, Na, LDH), platelet counts, haemoglobin counts as well as review of adverse events and serious adverse events. Measurements of treatment response, health-related quality of life, and other measurements of efficacy per SOC will be collected.

In this study approximately 126 patients will participate. They will be enrolled in 30 study sites from Spain, United Kingdom and Italy.

i. Disease

Primary Immune thrombocytopenia

j. Study outcome measures

Primary outcome measure:

To evaluate the difference between study arms in the proportion of patients achieving 6mSROT-50 at 6 months (180 days) from treatment cessation.

Definition of 6mSROT-50: platelets higher or equal than 50x10⁹/L in the absence of any ITP treatment including any rescue treatment for at least 6 consecutive months (≥180 days) from treatment cessation and without WHO grade 2 or more bleeding.

Secondary outcome measures:

- To evaluate the difference between study arms in the proportion of patients achieving 6mSROT-30 at 6 months (180 days) from treatment cessation.
 - Definition of 6mSROT-30: platelets higher or equal than 30x10⁹/L
 in the absence of any ITP treatment including any rescue treatment
 for at least 6 consecutive months (≥180 days) from treatment
 cessation and without WHO grade 2 or more bleeding.

- To evaluate the difference between study arms in the proportion of patients achieving 12mSROT-50 at 12 months (365 days) from treatment cessation.
 - Definition of 12mSROT-50: platelets higher or equal than 50x10⁹/L
 in the absence of any ITP treatment including any rescue treatment
 for at least 12 consecutive months (≥365 days) from treatment
 cessation and without WHO grade 2 or more bleeding.

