Study time point	Days -28 to -1	Day 1	Weekly visits until Week 7	Week 8	Weekly or biweekly visits until Week 14 ¹¹	Week 16 and week 20	Week 24 (Month 6)	Monthly visits until Month 11	Month 12	Monthly visits until Month 17 ¹²	Month 18 ¹²	Unscheduled visit
			±1 days	±1 days	±1 days	±3 days	±7 days	±3 days	±7 days	±7 days	±7days	
Eligibility criteria	Х	Х										
Informed consent ¹	Х											
Medical history ³	Х											
Demographics ²	Х											
Pregnancy test ⁴	Х											
Randomization		Х										
Vital signs ⁵	Х	Х	Х	Х	X ⁵	Х	Χ	Х	Х	X	Х	X
Physical examination ⁶	Χ	Х	X ⁶	Х	X _e	Х	Х	Х	Х	Х	Х	X
Laboratory tests ⁷	Χ	Х	Х	Х	Х	Х	Х	Х	Х	X	Х	Х
WHO Bleeding score	Х	Χ	Х	Χ	Х	Х	Χ	Х	Х	X	X	X
HRU and loss of productivity8		Χ	X	Χ	X	Χ	Χ	X	Χ	X	Χ	
Quality of life questionnaires:9 SF36, FACIT, ITP PAQ		Χ		Χ			X		Χ		Χ	
ITP-BAT ¹⁰	Х	Χ		Χ	X ¹⁰		Χ		Х		X	
ITP medication		Χ	Х	Х	Х	Х	Χ	Х	X			
Rescue medication		Х	Х	Х	Х	Х	Х	Х	Х			Х
Concomitant medication		Χ	Х	Χ	X	Х	Χ	Х	X	X	Χ	X
AEs/Bleeding event reporting//splenectomy		Х	Х	Х	Х	Х	Х	Х	Х	Х	Х	Х

- 1. Informed consent must be signed and dated prior to any study-related procedure and before any data is recorded in the CRF.
- 2. Demographic data collection including sex, age, and ethnicity.
- 3. Medical history includes all information related to a new diagnosis of ITP and bleeding events history.
- 4. The pregnancy test at screening will be conducted 72 hours before first dose of study treatment.
- 5. Vital signs includes respiratory rate, body temperature, blood pressure, and pulse rate. They must be measured every week until week 8, then every 4 weeks.
- 6. Physical examination will be performed as per standard of care. Physical measurements include height (at screening) and weight (at screening, baseline and from then on every 4 weeks+/- 1 week). There shall be no dose adjustments until changes of 10% or more in weight.
- 7. Complete blood counts with differential, blood chemistry profiles (serum creatinine, ALT, AST, GGT, K, Na, LDH) and platelet counts.
- 8. HRU and loss of productivity shall be measured monthly.
- 9. Quality of life (SF36 v2, FACIT-F and IPT-PAQ) will be evaluated at Day 1, week 8, Month 12 and End of study Visit (visit 12 months after the last dose of study treatment).
- 10. ITP-BAT will be evaluated to screening, Day 1, Week 8, Week 12, Month 6, Month 12 and End of study Visit (visit 12 months after the last dose of study treatment).

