- Investigator will collect lactation information on any female subject who breastfeeds while taking protocol-required therapies through 30 days after last dose of IP.
- Information will be recorded on the Lactation Notification Worksheet and submitted to Sponsor within 24 hours of the investigator's knowledge of event.
- Study treatment will be discontinued if female subject breastfeeds during the study.
- With the female subjects signed authorization for release of mother and infant health information, the investigator will collect mother and infant health information and complete the lactation questionnaire on any female subject who breastfeeds while taking protocol- -required therapies through 30 days after discontinuing protocolrequired therapies.

Annex 6. Hepatotoxicity Stopping Rules: Suggested Actions and Follow-up Assessments and Study Treatment Rechallenge Guidelines

Subjects with abnormal hepatic laboratory values (i.e., alkaline phosphatase [ALP], aspartate aminotransferase [AST], alanine aminotransferase [ALT], total bilirubin [TBL]) and/or international normalized ratio (INR) and/or signs/symptoms of hepatitis (as described below) may meet the criteria for withholding or permanent discontinuation of study therapies, as specified in the *Guidance for Industry Drug-Induced Liver Injury: Premarketing Clinical Evaluation, July 2009.*

Criteria for Withholding and/or Permanent Discontinuation of Protocol-required Therapies Due to Potential Hepatotoxicity

The following stopping and/or withholding rules apply to subjects for whom another cause of their changes in liver biomarkers (TBL, INR and transaminases) has not been identified.

Important alternative causes for elevated AST/ALT and/or TBL values include, but are not limited to:

- Hepatobiliary tract disease
- Viral hepatitis (e.g., hepatitis A/B/C/D/E, Epstein-Barr Virus, cytomegalovirus, herpes simplex virus, varicella, toxoplasmosis, and parvovirus)
- Right sided heart failure, hypotension or any cause of hypoxia to the liver causing ischemia
- Exposure to hepatotoxic agents/drugs or hepatotoxins, including herbal and dietary supplements, plants and mushrooms
- Heritable disorders causing impaired glucuronidation (e.g., Gilbert's syndrome, Crigler-Najjar syndrome) and drugs that inhibit bilirubin glucuronidation (e.g., indinavir, atazanavir)
- Alpha-one antitrypsin deficiency
- Alcoholic hepatitis
- Autoimmune hepatitis
- Wilson's disease and hemochromatosis

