- Nonalcoholic fatty liver disease including steatohepatitis (NASH)
- Non-hepatic causes (e.g., rhabdomylosis, hemolysis)

If investigational product(s) is/are withheld, the subject is to be followed for possible druginduced liver injury (DILI) according to recommendations in the last section of this appendix. Rechallenge may be considered if an alternative cause for impaired liver tests (ALT, AST, ALP) and/or elevated TBL, is discovered and the laboratory abnormalities resolve to normal or baseline (see next section in this appendix).

Table 12-2. Conditions for Withholding and/or Permanent Discontinuation of Protocol-required Therapies Due to Potential Hepatotoxicity

Analyte	Temporary Withholding	Permanent Discontinuation
TBL	> 3x ULN at any time	> 2x ULN
		OR
INR		> 1.5x ULN (for subjects not on anticoagulation therapy)
	OR	AND
AST/ALT	> 8x ULN at any time > 5x ULN but < 8x ULN for ≥ 2 weeks > 5x ULN but < 8x ULN and unable to adhere to enhanced monitoring schedule > 3x ULN with clinical signs or symptoms that are consistent with hepatitis (such as right upper quadrant pain/tenderness, fever, nausea, vomiting, and jaundice) OR	In the presence of no important alternative causes for elevated AST/ALT and/or TBL values > 3x ULN (when baseline was < ULN)
ALP	> 8x ULN at any time	

ALP = alkaline phosphatase; ALT = alanine aminotransferase; AST = aspartate aminotransferase; INR = international normalized ratio; TBL = total bilirubin; ULN = upper limit of normal.

Criteria for Rechallenge of Protocol-required Therapies After Potential Hepatotoxicity

The decision to rechallenge the subject is to be discussed and agreed upon unanimously by the subject, investigator, and the sponsor.

If signs or symptoms recur with recalling, then IP is to be permanently discontinued. Subjects who clearly meet the criteria for permanent discontinuation (as described in Table 12-2) are never to be rechallenged.

Reporting

To facilitate appropriate monitoring for signals of DILI, cases of concurrent AST or ALT and TBL and/or INR elevation, according to the criteria specified in the above, require the following:

- The event is to be reported to Sponsor as a serious adverse event within 24 hours of discovery or notification of the event (i.e., before additional etiologic investigations have been concluded)

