- The appropriate CRF (e.g., Event CRF) that captures information necessary to facilitate the evaluation of treatment-emergent liver abnormalities is to be completed and sent to Sponsor

Other events of hepatotoxicity and potential DILI are to be reported as serious adverse events if they meet the criteria for a serious adverse event.

Additional Clinical Assessments and Observation

All subjects in whom investigational product(s) or protocol-required therapies is/are withheld (either permanently or conditionally) due to potential DILI as specified in Table 12-2 or who experience AST or ALT elevations > 3 x upper limit of normal (ULN) or 2-fold increases above baseline values for subjects with elevated values before drug are to undergo a period of "close observation" until abnormalities return to normal or to the subject's baseline levels. Assessments that are to be performed during this period include:

- Repeat AST, ALT, ALP, bilirubin (total and direct), and INR within 24 hours
- In cases of TBL > 2x ULN or INR > 1.5, retesting of liver tests, bilirubin (total and direct), and INR is to be performed every 24 hours until laboratory abnormalities improve Testing frequency of the above laboratory tests may decrease if the abnormalities stabilize or the investigational product(s) or protocol-required therapies has/have been discontinued and the subject is asymptomatic.

Initiate investigation of alternative causes for elevated AST or ALT and/or elevated TBL. The following are to be considered depending on the clinical situation:

- Complete blood count (CBC) with differential to assess for eosinophilia
- Serum total immunoglobulin IgG, anti-nuclear antibody (ANA), anti smooth muscle antibody, and liver kidney microsomal antibody -1 (LKM1) to assess for autoimmune hepatitis.
- Serum acetaminophen (paracetamol) levels.
- A more detailed history of:
 - Prior and/or concurrent diseases or illness.
 - o Exposure to environmental and/or industrial chemical agents.
 - Symptoms (if applicable) including right upper quadrant pain, hypersensitivity-type reactions, fatigue, nausea, vomiting and fever.
 - o Prior and/or concurrent use of alcohol, recreational drugs and special diets.
 - Concomitant use of medications (including non-prescription medicines and herbal and dietary supplements), plants, and mushrooms.
- Viral serologies.
- Creatine phosphokinase (CPK), haptoglobin, lactate dehydrogenase (LDH), andperipheral blood smear.

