- · Appropriate liver imaging if clinically indicated.
- Appropriate blood sampling for pharmacokinetic analysis if this has not already been collected.
- Hepatology consult (liver biopsy may be considered in consultation with a hepatologist).

Follow the subject and the laboratory tests (ALT, AST, TBL, INR) until all laboratory abnormalities return to baseline or normal or considered stable by the investigator. The "close observation period" is to continue for a minimum of 4 weeks after discontinuation of all investigational product(s) and protocol-required therapies.

The potential DILI event and additional information such as medical history, concomitant medications and laboratory results must be captured in the corresponding CRFs.

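### Annex 6 withholds treatment on bilirubin or ALP alone, but the scheduled chemistry panel measures neither

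*Protocol*

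**What the plan says.** The scheduled chemistry panel is stated four times with the same content. Table 3, note 7, gives "blood chemistry profiles (serum creatinine, ALT, AST, GGT, K, Na, LDH) and platelet counts" for each arm. Section 1.h and section 6.a give "blood chemistry profiles (serum creatinine, ALT, AST, GGT, K, Na, LDH), platelet counts, haemoglobin counts". Each is a closed list, and none contains total bilirubin (TBL) or ALP.

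Annex 6, Table 12-2, sets the conditions for withholding or stopping treatment for possible hepatotoxicity:

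- **Temporary withholding:** TBL "> 3x ULN at any time", or one of several AST/ALT conditions, or ALP above 8x ULN at any time.
- **Permanent discontinuation:** TBL above 2x ULN or INR above 1.5x ULN, together with AST/ALT above 3x ULN.

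Annex 6 orders TBL and ALP only within a period of close observation. Patients enter it when treatment is withheld under Table 12-2, "or who experience AST or ALT elevations > 3 x upper limit of normal (ULN) or 2-fold increases above baseline values" where the values were already raised before drug. The first action is then "Repeat AST, ALT, ALP, bilirubin (total and direct), and INR within 24 hours".

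Rechallenge may be considered if another cause "is discovered and the laboratory abnormalities resolve to normal or baseline". The closing instruction is "Follow the subject and the laboratory tests (ALT, AST, TBL, INR) until all laboratory abnormalities return to baseline or normal", or are judged stable by the investigator.

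**The concern.** Two parts of the protocol do not fit together. Annex 6 makes TBL and ALP triggers that need no transaminase rise, but the visit schedule never obtains either value. A threshold that applies at any time is of little use if nothing in the schedule measures the analyte.

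What is at stake is patient safety, mainly in the romiplostim arm, where dosing can last a year. A patient with predominantly cholestatic injury could go on being dosed although the protocol's own rule says to withhold. A second problem is that a raised TBL found later would have no scheduled pre-treatment value to show whether the rise is new.

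**Working it through.** The protocol states no figure to reproduce. The check compares the analytes the rules need with the analytes the schedule supplies.

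**1. Analytes in the temporary-withholding column of Table 12-2**

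| Analyte | Stand-alone trigger | In scheduled panel |
|---|---|---|
| AST/ALT | Yes (several conditions) | Yes |
| TBL | Yes, above 3x ULN | No |
| ALP | Yes, above 8x ULN | No |

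Two of the three are never measured by schedule. GGT is scheduled, but no rule in Annex 6 acts on it.

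**2. Protocol-specified routes to a TBL or ALP result**

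- *Route A:* AST/ALT above 3x ULN, or a doubling from a raised baseline. This requires a transaminase rise.
- *Route B:* drug already withheld under Table 12-2. If the reason is TBL or ALP, the route is circular, because the value must be known before drug can be withheld for it. If the reason is AST/ALT, every condition in that row is at least 3x ULN, so it falls within Route A.

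On scheduled tests, both routes therefore start from AST/ALT.

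**3. What this leaves covered and uncovered**

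- *Covered:* the permanent-discontinuation rule. Its AST/ALT condition itself starts TBL and INR testing.
- *Covered:* TBL above 3x ULN or ALP above 8x ULN when AST/ALT has also met an entry condition.
- *Uncovered:* TBL above 3x ULN or ALP above 8x ULN when AST/ALT has met neither entry condition.

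**4. Extent in the romiplostim arm (Table 3)**

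Visits from screening to Month 12: Visit 0 (1) + Visit 1 (1) + Visits 2–8 (7) + Visit 9 (1) + Visits 10–16 (7) + Visits 17–18 (2) + Visit 19 (1) + Visits 20–24 (5) + Visit 25 (1) = 26. Laboratory tests are marked at all 26; TBL and ALP are listed at 0 of 26. Dosing can run to Day 365.

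**5. Extent in the DEX arm**

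There are three cycles of 4 days, at a longest interval of 28 days.

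- Interval counted start to start: cycles begin on Days 1, 29 and 57, so the last dose is on Day 57 + 3 = 60.
- Interval counted from end of one cycle to start of the next (an assumption): cycles begin on Days 1, 4 + 28 = 32 and 35 + 28 = 63, so the last dose is on Day 63 + 3 = 66.

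Withholding can affect only cycles 2 and 3.

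**6. Baseline**

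Annex 6 asks for ALP and bilirubin to be repeated, and several of its endpoints refer to baseline, yet no earlier value is scheduled. The eligibility criteria (section 7.b) set no bilirubin limit, so patients with raised TBL can enter. Annex 6 itself names "Heritable disorders causing impaired glucuronidation" among the alternative causes. In such a patient TBL may never reach normal, and the baseline that would serve instead is unknown.

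**The case against.** The strongest reply is that the two texts do not contradict each other. Annex 6 is titled as suggested actions and says what to do once an abnormal value is known; it does not order routine measurement. The schedule also has other ways to raise suspicion: GGT, physical examination and adverse-event review on treatment, with laboratory tests also allowed at unscheduled visits. An investigator may stop treatment for an adverse event (section 8.b). Eligibility already relies on tests outside note 7, such as INR and viral status, so note 7 may not list all laboratory work. The TBL and ALP thresholds are multiples of ULN and need no baseline, and the recovery endpoints accept normal as an alternative. The rules do not apply where another cause has been identified, which covers known impaired glucuronidation. No hepatic event is among the romiplostim events of special interest (section 10.c.vii), and active or severe liver disease is excluded.

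Much of this narrows the consequence. A clinician may well test a jaundiced patient or follow up a raised GGT, and some sites may measure TBL at screening. It does not close the gap. The protocol requires neither test in the uncovered case, and it calls adherence to the schedule essential. Softer wording about actions does not supply the measurement on which a threshold depends. The baseline point is secondary. Its force is limited to patients whose TBL was already raised, particularly where the cause had not been diagnosed.

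**Conclusion.** The concern holds. Two of the three analytes that can trigger temporary withholding are not scheduled at any visit. On scheduled tests their stand-alone triggers cannot be reached unless AST/ALT has already risen. The gap is narrow: isolated TBL above 3x ULN or ALP above 8x ULN, mainly over up to 365 days of romiplostim dosing, and only to about Day 60–66 in the DEX arm.

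The conclusion rests on reading the links in Table 12-2 as making TBL and ALP sufficient on their own, which is the natural reading, and on taking the four identical panel lists as complete. The documents give no rate for such isolated rises, so no expected number of missed cases can be given. Sample size, power and the primary analysis are unaffected. The change should be made, as a matter of safety monitoring.

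**What to change.** Add total bilirubin and ALP to the chemistry panel in Table 3, note 7, for both arms, and to the matching text in sections 1.h and 6.a. Include screening or Day 1, so that each patient has a pre-treatment value. Leave the Table 12-2 thresholds unchanged. INR need not be added: it appears only in the combined permanent-discontinuation rule, whose AST/ALT condition already starts INR testing.

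Deleting the two stand-alone triggers would also remove the inconsistency, but by weakening the safety rule.

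The cost is a protocol amendment (section 13.d) across about 30 sites in three countries, two further analytes on chemistry samples already drawn, and some incidental abnormal values to follow up. No new visit or tube is needed. Patients already on treatment would gain monitoring from then on, but not a baseline.

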10. ASSESSMENT OF SAFETY / ADVERSE EVENTS

Safety information should be collected in clinical studies in an efficient and consistent way. Adverse events must be identified and notified rapidly to identify possible risks to patients and satisfy regulatory requirements for notification of adverse events. Safety reporting requirements to both Amgen and to Regulatory Agencies are specified. All reporting obligation to the Regulatory Authorities will be written and send.

a. **Definitions** [49]

i. Adverse event (AE)

An AE is any untoward medical occurrence in a patient participating in clinical research that is associated in time with the use of a medicinal product, whether or not it is considered to be related to the investigational products. Therefore, an adverse event can be any unfavourable and unintended sign (including an anomalous laboratory result), symptom or disease that is associated in time with the use of a medicinal product, whether or not it is considered to be related to the product. Pre-existing or underlying diseases that worsen during the study, or events associated with the discontinuation of the use of a product(s) (e.g. appearance of new symptoms), shall be notified as Adverse Events.

AEs include pre- or post-treatment events that occur as a result of study procedures (e.g. invasive procedures or modification of the patient's previous medication).

ii. Serious adverse event (SAE)

A SAE is an undesired medical experience that, at any dose:

- Results in death.
- Is life-threatening: (NOTE: The term "life-threatening" refers to the fact that, according investigator criteria, the patient is at risk of death as a result of this

- event. Nevertheless, this definition does not consider the situation in which if the AE had been more severe, patients had been in an immediate risk of death).
- Results in the patient's hospitalization or prolongs a previous hospitalization (NOTE: In general, hospitalization means that the patient has remained [at least 24 hours] in the hospital or emergency visits. Complications that occur during a hospitalization are AEs. If a complication prolongs hospitalization or satisfies any of the other criteria for seriousness, then the event will be considered SAE. When any doubt exists as to whether a "hospitalization" has taken place or was necessary, the AE will be considered serious. The hospitalization to implement scheduled treatment of a disease present before the subject entered the study and that has not worsened with respect to baseline is not considered an AE. Hospitalizations for social reason are not considering an AE.
- It produces disability or incapacity (NOTE: Disability refers to an important alteration in a person's capacity to carry out his or her own daily living tasks, not minor clinical ailments such as headaches, nausea, vomiting, diarrhoea, flu or accidental injuries (such as a sprained ankle), that can interfere with the functions of daily life, but do not alter them in an important way).
- It originates a congenital anomaly or birth defect.
- It is medically important, meaning medically important adverse event that the
 investigator regards as serious that did not strictly meet the criteria above but may
 have jeopardized the patient or required intervention to prevent one of the
 outcomes listed above, or that would suggest any significant hazard,
 contraindication, side effect, or precaution that may be associated with the use of
 the investigational medicinal product.

iii. Adverse reaction

Any harmful and non-intended response to a drug including adverse reactions derivative from any use apart from terms of commercialization authorization, abuse, and medication error. It exist a confirmed causality relationship with the administered medication.

iv. Product Complaints

Any written, electronic or oral communication that alleges deficiencies related to the identity, quality, durability, reliability, safety, effectiveness, or performance of a drug, combination product, or device after it is released for distribution to market or clinic by either: (1) Amgen or (2) distributors or partners for whom Amgen manufactures the material. This includes all components distributed with the drug, such as packaging, drug containers, delivery system, labelling, and inserts.

Examples include:

- Device that is damaged or broken
- Bent or blunt needles
- Missing or illegible labeling

- Inability of customer to administer the product
- Product with an unexpected color, appearance, or particles
- Use error (i.e., an act or omission of an act that results in a different combination product or medical device response than intended by the manufacturer or expected by the user, where the user attempted to use the combination product or medical device in good faith and experienced difficulty or deficiency administering the product).

b. Characteristics of an adverse event

i. Seriousness

See Serious Adverse Event definition (11.1.2 Serious Adverse Event (SAE)).

ii. Causality assessment

The investigator has the obligation to establish the relation of causality between the investigational product administration and the adverse event (serious or not). "A reasonable possibility" is proposed to define cases in which there are facts/proof or arguments suggesting a causal relation, more than a relation that cannot be excluded. The investigator will use his or her clinical judgment to determine the relation. Alternative causes, such as the natural history of underlying diseases, concomitant treatment, other risk factors and the temporal relation between the event and the investigational drug will be considered and investigated. The investigator will also consult the investigator's brochure/summary of product characteristics in making the evaluation.

There may be situations in which a SAE occurs and the investigator has only minimal information to include in the initial report to the Sponsor. Nevertheless, it is very important that the investigator evaluate the causality of each event before the initial transmission of data to the Sponsor. The investigator can change his or her opinion about causality based on the information that appears during follow-up, which is why the SAE report may have to be modified. The evaluation of causality is one of the criteria that determine whether a case is compliant or not with the criteria of notification of the Health Authorities.

iii. Expectedness

An unexpected adverse reaction is any untoward and unintended response that is related to the administration of the study drug at any dose that is not consistent with the applicable product information (e.g., investigators brochure for an unauthorized investigational medicinal product or summary of product characteristics for an authorized product).

CRO/Sponsor will classify an Adverse Reaction as expected or unexpected according to the Reference Safety Information collected in investigator brochure or summary of product characteristics of investigational product, as appropriate. The Reference Safety Information is considered "expected" for regulatory reporting purposes by the Sponsor.

iv. Severity

The severity of any AEs will be graded using the CTCAE vs 5.0 (see Annex 4). If the CTCAE has no code that matches, the following guide should be used:

Grade	Description
0	No adverse event
1	Mild; asymptomatic or mild symptoms; clinical or diagnostic observations only
2	Moderate; minimal, local or non-invasive intervention indicated
3	Severe or medically significant but not immediately life-threatening; hospitalization or prolongation of hospitalization indicated
4	Life-threatening consequences; urgent intervention indicated
5	Death related to adverse event

Grading of AEs is based on specific clinical criteria that will require evaluation by the study site Investigator. Should an AE stop and then restart, it will be considered two separate events and the severity assessed as described above.

v. Additional considerations

Alterations in laboratory parameters (haematology, biochemistry or urine analysis), as well as anomalous results of other studies (such as ECGs, radiology, measurements of vital constants), including those that deteriorate in relation to baseline, should be recorded as AEs or SAEs if, in the medical and scientific opinion of the investigator, they are clinically relevant.

On the contrary, clinically significant alterations in safety parameters that are associated with the study disease are not characterized as AEs or SAEs unless the investigator thinks that they are more serious than would be expected considering the state of the patient.

Lack of efficacy is a disease-related event and should not be classified as a SAE.

Since, according to patient profile and current clinical practice, the starting dose of romiplostim will be 3 mcg/kg instead of 1 mcg/kg as indicated in the label, close monitoring of potential safety concerns will be conducted.

c. Reporting procedures

i. Reporting of adverse events (AEs)

The investigator will try to obtain information about any adverse events that have occurred in all visits by examining or directly interrogating the patient.

All information referring to adverse events must be recorded in the respective section of the CRF. AEs should be recorded according CTCAE v 5.0. All adverse events that occur during the period comprehended from the time of enrolment of the patient in the study (signing of the consent form) to 30 days after last dose of the investigational products will

be recorded. When one or more signs or symptoms correspond to a disease, the main diagnosis or syndrome will be notified. All adverse events will be followed until resolution or stabilization, or until it is determined that the study treatment or the patient's participation in the study has not been the cause. All adverse events still present at the end of the study period will be monitored until their final outcome is determined.

ii. Reporting of serious adverse events (SAEs)

All serious adverse events that occur during the clinical trial, whether or not they are related to the study drug, must be communicated immediately by e-mail or by fax within 24 h of receiving knowledge of the same or, at the latest, on the next working day at:

Unidad de Investigación Clínica y Ensayos Clínicos
Hospital Universitario Virgen del Rocío
Dpto. Farmacovigilancia
Email: [contact]
[name]
[name]
[contact]

[contact]

The investigator will collect information about the SAE on the respective form. At least these **four elements are mandatory** always to report any adverse event:

- Name or any identifier of a reporter
- **Subject** ID number
- At least one **suspect drug**: current dose, route, dates
- Adverse Event information:
 - Adverse Event Term Seriousness Criteria
 - o Adverse event outcome
 - Causality assessment

iii. Expectedness

IMP	RSI to be used for expectedness assessment	Relevant section to be used for expectedness assessment
Romiplostim	Amgen Romiplostim SPC Amgen Romiplostim IB	Section 4.8 Section 7.6
Dexamethasone	TAD Pharma Dexamethasone SPC	Section 4.8

iv. Reporting of serious adverse events (SAEs) to Health Authorities

The sponsor is responsible for notifying to the Health Authorities of all suspected serious adverse reactions and unexpected, which occurred in the clinical trial. This communication shall be made within the time limits established by current legislation.

v. Follow-up of AEs and SAEs

After the initial notification of an AE or SAE, the investigator is required to follow up each case and obtain more data on the patient's state. All the AEs and SAEs documented in previous visits must be reviewed in subsequent visits. All AEs and SAEs must be monitored until their resolution. This is applicable to all the patients, including those who withdraw early.

The investigator will include in the follow-up any additional research that may clarify the nature and/or causality of the AE or SAE. This might include additional laboratory tests or studies, histopathologic examinations, or the consultation of other healthcare professionals. Any co-investigator can ask the investigator to carry out additional evaluations to definitively clarify the nature and/or the causality of AEs or SAEs. If the patient dies while participating in the study or during a follow-up period agreed upon mutually, the investigator will provide a copy of any post-mortem finding requested, including histopathology.

vi. AEs or SAEs that occur after the study ends

Post-study AEs or SAEs are defined as any event that occurs outside the Follow-up period of detection defined in the protocol. The investigator is not required to actively seek out AEs or SAEs in patients who have participated in the clinical trial in the past. Nevertheless, if the investigator comes to know of the existence of any AE or SAE, including the death of the patient at any time after a patient has left the study, and this AE or SAE is considered related to the study drug, the investigator must notify the sponsor promptly.

vii. Adverse Events of special interest (AESIs)

An AESI is an adverse event of scientific and medical concern specific to the study treatment in order to obtain a greater knowledge about its safety profile. The AESIs can be severe or not.

Any AE (serious or non-serious) that is of scientific and medical concern specific to the study treatment, for which ongoing monitoring and rapid communication by the Investigator to SPONSOR. Early notification allows a continuous monitoring of these events in order to be characterized and understood in relation with the use of study drug.

Adverse Events of Special Interest (AESIs) for romiplostim are the following:

- Haemorrhage
- Thrombotic/thromboembolic events
- Progressing existing myelodysplastic syndrome (MDS)
- Neutralizing antibodies that cross react with eTPO

- Haemolytic anaemia
- Interstitial lung disease and pulmonary fibrosis
- Non-haematological malignancies

When the patient begins the treatment with romiplostim, any event that is categorized as a romiplostim AESI, would need to be reported as AESI even if it is non-serious. AESI notification is irrespective of the severity/grade of event and relationship to romiplostim.

viii. Timeframes for Submission of Safety Data to Amgen

Regarding the timeframes for submission of Safety Data to Amgen the information of the next tables must be followed (Table 4 and Table 5).

Table 4. For interventional studies with Amgen IMPa

Safety Data	Timeframe for submission to Amgen	Send to
Suspected Unexpected Serious Adverse Reaction (SUSARs)	At time of regulatory submission	Amgen Safety
Pregnancy/Lactation exposure and any associated reports/outcomes (i.e. unexpected pregnancy, pregnancy of partner, spontaneous abortion, congenital anomaly etc.)	Within 1 business day of Sponsor awareness, for reports meeting serious criteria Not to exceed 15 calendar days of Sponsor awareness, for non-serious reports	Amgen Safety

^a Specific requirements are to be outlined in the Research Agreement.

Table 5. Adverse Device Effects for Amgen-marketed devices and device constituents in combination products^{b,c} and Product complaints:

Safety Data	Timeframe for submission to Amgen	Send to
Unanticipated Serious Adverse Device Effects, (USADEs), Serious Adverse Device Effects (SADEs) and Non- serious Adverse Device Effect (Non-serious ADEs)	Within 1 business day of Sponsor awareness	Amgen Safety
Product Complaints ^c	Within 1 business day of Sponsor awareness	Amgen Quality

Specific requirements are to be outlined in the Research Agreement. Requirements in the table should ALWAYS be included, regardless if the Amgen device/combination product is being studied used in the study or if the device/combination product is used as standard of care in the study.

^aAmgen combination products and devices that are marketed anywhere in the world (regardless of the status of the combination product/device in the country where the study is carried out).

^b Adverse device effect (ADE) is any adverse effect caused by or associated with the use of a device constituent of a combination product or medical device. Adverse device effects include, but are not limited to, adverse effects resulting from insufficient or inadequate instructions for use, any malfunction of the device, or use error or intentional misuse of the device.

